Interested participants will fill out a brief questionnaire to confirm eligibility either online or over the phone with research staff. Participants will be asked a series of questions regarding their tobacco product usage, health status, willingness to travel to Columbus for study visits, and brief demographic and contact information. Research staff will review the screener questionnaire for eligibility and inform participants if they are eligible for this study or not. Research staff will provide a study overview, discuss study procedures, and ascertain participant interest. Should the participant wish to proceed, research staff will schedule the first visit and communicate IRB-approved guidance, such as the CTR address and the need for subjects to abstain from tobacco products for 12 hours prior to the study visit. Participants will be advised that each research visit must be scheduled 2 or more days apart and that they must bring their own brand of cigarettes to the study visits in case they are randomized to smoke cigarettes at a particular visit.

Clinic Visits

Aim 1: Participants will be invited to the CTR to complete study procedures. At visit 1, informed consent will be collected. During visits 1-3, participants will complete an exhaled CO test, take a pregnancy test if applicable, a line will be placed for IV blood draw by the staff research nurse for IV blood draws throughout the course of the study visit, and be asked to either smoke their usual brand or insert a 3mg or 6mg NP and then sit in the room for 60 minutes. At each visit, participants will be randomly assigned to use 3mg Wintergreen pouches, 6mg Wintergreen pouches or their own brand of cigarettes. Participants will be asked a series of 3 questionnaires before, during, and after each product is used. Blood draws will be collected from the line at 0 5, 15, 30, 60, and 90-minutes. 3mLs, or a little less than 1 teaspoon, of blood will be drawn at each timepoint.

Measures of craving and withdrawal relief will be assessed at each blood draw (see attached surveys). If a collection interval is not met there will be no draw retroactively. Participants will be assessed for AE throughout procedures and prior to leaving the visit.

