Participants will need to abstain from tobacco and nicotine products for ≥ 12 hours prior to their study visit. To check for abstinence from tobacco, participants will perform exhaled carbon monoxide testing ($eCO < 10\text{ppm}$) and confirm via self-report that they have not used any other nicotine products over the last 12 hours.

Pregnancy Test

All subjects capable of becoming pregnant will need to take and produce a negative pregnancy test in order to proceed further.

Pre-intervention questionnaire to be administered

This questionnaire will assess sociodemographics, tobacco use history, NP use history, and nicotine dependence. These questionnaires will be administered during Visit 1.

IV line insertion

Because blood draws will occur at set intervals, an IV line will be inserted by a trained staff nurse.

Blood draw to obtain baseline plasma nicotine levels

Next, participants will be reminded that in addition to the exhaled CO test, their abstinence will be confirmed at the time of visit via blood plasma nicotine analysis. 3 mL venous blood sample will be collected for later analysis to confirm abstinence. This blood draw will also be used to establish baseline plasma nicotine levels to estimate total nicotine delivery.

Administer intervention

Aim 1: The participant will receive a 3mg NP, 6mg NP, or be asked to smoke one cigarette of their usual brand depending on the randomization assignment. If smoking a cigarette, participants will be asked to smoke one cigarette following a standardized puffing protocol: they will take one puff every 30 seconds for 5 minutes. If using an NP, participants will be asked to place the pouch between their upper lip and gum and leave it in place for 30 minutes.

Aim 2: The participant will receive a 3mg tobacco-derived NP or a 3mg synthetic NP on randomization assignment. Participants will be asked to place the pouch between their upper lip and gum and leave it in place for 30 minutes.

Peri-intervention questionnaire to be administered

The QSU and MNWS surveys will be administered while at each blood draw interval of 0, 5, 15, 30, 60, and 90 minutes.

Post-intervention questionnaire to be administered

Measures of product appeal and behavioral intentions will be assessed after the participant has the cigarette or NP (Aim 1) or the tobacco-derived vs. synthetic NP (Aim 2).

Schedule return visit and provide gift card for participation

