Data will be summarized descriptively. For hypothesis testing, we will use linear or logistic mixed effects regression models (with a random subject effect) to assess the main effects of product on plasma nicotine delivery, subjective effects, and behavioral intentions. Model assumptions will be checked, and variables will be transformed as needed. Missing data will not be imputed as likelihood-based linear mixed models will yield valid inference under missing at random assumptions. Models will control for age, sex, and other tobacco use if these features are not balanced by randomization. The same analysis strategy will be used for both aims. We calculated power for Aim 1 based on a repeated measures ANOVA comparing mean total nicotine delivery and maximum plasma nicotine concentration across 3 conditions; existing literature on differences in nicotine delivery across SLT products, including NPs, facilitates the use of this outcome for a power analysis.⁹ With a total sample size of only 20 participants and a Bonferroni-adjusted alpha of 0.017, we would have 84% power to detect a mean difference in total nicotine delivery of 25.7 ng/mL and 99% power to detect a mean difference of maximum nicotine concentration of 7.0 ng/mL between products.⁹ To account for attrition and the potential need for a larger sample size to detect differences in more subjective outcomes, we will recruit a

sample of 40 participants. For Aim 2, there are no known data to estimate effect sizes and thus to conduct power analyses. The sample size of 15 participants is intended to provide these data for future research.

5. Safety Management, Risks, and Benefits

Safety Management

Clinical Adverse Events

Clinical AE will be assessed by study staff at each study visit via participant self-report and managed immediately. Clinical AE may be related to nicotine overdose or the blood draw. Signs of nicotine overdose include nausea, vomiting, headache, presyncope, tachycardia, and disrupted sleep. With the blood draw, there is a slight risk of bruising, discomfort, and infection with blood draw. Study staff will be trained to recognize these signs and subjects will be encouraged throughout the visit to self-report any AE. In the event of a medical emergency, study staff will be advised to call 911 on the subject's behalf.

AE Reporting

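### A subject-only random effect does not hold the error rate for measures taken six times per visit, and the missing-at-random reason does not reach a draw missed inside a visit total

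*Combined protocol and SAP*

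**What the plan says.** Statistical Considerations (section 4) plans "linear or logistic mixed effects regression models (with a random subject effect) to assess the main effects of product on plasma nicotine delivery", and applies the same models to subjective effects and behavioural intentions in both aims. Subject is the only random term. Neither a time term nor a within-visit covariance is stated. On missing data it says "Missing data will not be imputed as likelihood-based linear mixed models will yield valid inference under missing at random assumptions".

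The power text in the same section describes a "repeated measures ANOVA comparing mean total nicotine delivery and maximum plasma nicotine concentration across 3 conditions", which implies one value per participant per product.

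Clinic Visits (section 2), for each aim, schedules six draws per visit and adds "If a collection interval is not met there will be no draw retroactively". Study Procedures (section 3) says "The QSU and MNWS surveys will be administered while at each blood draw interval of 0, 5, 15, 30, 60, and 90 minutes", and says of the pre-use draw "This blood draw will also be used to establish baseline plasma nicotine levels to estimate total nicotine delivery". The plan gives no formula for that total, no per-visit summary of the two scales, and no rule for a visit with a missed draw.

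**The concern.** The plan measures at two levels: six times within a visit, and three visits within a participant. One random subject effect describes only the second. If the rows are draws, those from one visit share that visit's uptake, setting and mood. The subject-only model treats them as independent once the subject is allowed for.

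If the rows are visit totals, the difficulty moves to missing data. Likelihood methods handle a missing row under missing at random, but a total with one draw missing is neither a complete row nor, without a rule, a missing one.

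Hypotheses 1a and 1b rest on nicotine delivery and product appeal. Hypothesis 1a also concerns speed of delivery, which neither a total nor a maximum answers, so an analysis by draw is a natural choice. At stake are the error rate of the product comparisons and an avoidable loss of observed draws.

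**Working it through.** **Inputs from the documents.** N = 40 participants (Aim 1), K = 3 products, six draws per visit (five after baseline), level 0.017, subject as the only random term. **Assumed, because the documents give no values:** the within-visit correlation beyond the subject effect (ρ), the size of the time course, and the missed-draw rate.

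**1. The plan's own figures.** 0.05/3 = 0.0167, which rounds to the stated 0.017. The 84% and 99% power cannot be recomputed without a standard deviation. With 20 participants and a two-sided paired t test they imply standard deviations of the paired difference of about 31.4 and 6.1 ng/mL. Nothing shows them to be wrong.

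**2. Draw rows, time modelled.** Set the within-subject variance of a draw to 1, with share ρ due to the visit, and let T be the number of draws used. The visit-level mean square has expectation 1 + (T−1)ρ on 39 × 2 = 78 degrees of freedom. The rest of the residual has expectation 1 − ρ. The subject-only model pools the two:

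- residual df = 120T − 1 − 39 − 2 − (T−1), which is 554 for T = 5 and 673 for T = 6
- E = [78(1 + (T−1)ρ) + (df − 78)(1 − ρ)] / df
- R = (1 + (T−1)ρ) / E, the true variance of a product contrast over the variance the model reports
- actual rate = 2[1 − Φ(2.387/√R)], where 2.387 is the two-sided 0.017 normal point

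| T | ρ | 1+(T−1)ρ | E | R | Actual rate |
|---|---|---|---|---|---|
| 5 | 0.1 | 1.4 | 0.970 | 1.44 | 4.7% |
| 5 | 0.3 | 2.2 | 0.911 | 2.41 | 12.5% |
| 5 | 0.5 | 3.0 | 0.852 | 3.52 | 20.3% |
| 6 | 0.1 | 1.5 | 0.970 | 1.55 | 5.5% |
| 6 | 0.3 | 2.5 | 0.909 | 2.75 | 15.0% |
| 6 | 0.5 | 3.5 | 0.848 | 4.13 | 24.0% |

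Simulation with 20,000 null data sets per setting gives 4.6%, 12.6% and 20.0% (T = 5) and 5.5%, 14.8% and 23.9% (T = 6). A test that allows for the visit gives 1.6–1.8% on the same data. The plan does not say which level applies to the craving and withdrawal scales. At nominal 5% with five draws the simulated rates are about 10%, 20% and 30%.

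**3. Draw rows, no time term.** The time course then enters the residual. Let c be the standard deviation of the six time means, in units of a draw's within-subject standard deviation. For T = 6 and ρ = 0.3, df = 678 and E = (78 × 2.5 + 600 × 0.7 + 720c²)/678 = (615 + 720c²)/678.

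- c = 0.5: E = 1.173, R = 2.13, rate 10%
- c = 1: E = 1.969, R = 1.27, rate 3.4%
- c = 2: E = 5.155, R = 0.485, rate below 0.1%

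The direction of the error therefore depends on a term the plan does not state.

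**4. One complete value per visit.** With three rows per participant and a random subject effect, the simulated rate at nominal 1.7% was 1.2–1.95%. The model is adequate here.

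**5. Missed draws and visit totals.** If each draw is lost independently with probability m, a visit has a gap with probability 1 − (1 − m)⁶:

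- m = 1%: 6%, about 7 of the 120 Aim 1 visits
- m = 2%: 11%, about 14
- m = 5%: 26%, about 32
- m = 10%: 47%, about 56

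Voiding these visits gives no bias if loss is random, but it discards the draws that were taken. If loss depends on an earlier draw in the same visit, the draws are missing at random but the totals need not be, because that earlier draw is not in a model of totals. On assumed profiles, voiding then shifted the 6mg-minus-cigarette difference in total delivery by −1% to −14%, depending on how strong the dependence was.

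**The case against.** The power text works with one value per visit, for which a random subject effect is right, and nowhere does the plan say nicotine will be analysed by draw. A total left missing because it is not imputed is a missing row, and the stated reason then works under random loss. All draws in a visit come from one intravenous line, so losses probably cluster and void fewer visits than independence suggests. The plan says model assumptions will be checked, and the Procedure Manual, not available here, may hold rules for the blood measures.

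Much of this stands. Four stronger readings are tempting and are not supported:

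- **That the model is wrong for total delivery or maximum concentration as such.** For complete visit values it is adequate (step 4).
- **That the error rate is always inflated.** This holds with time modelled; without it the test can be conservative (step 3). Nor does subtracting a shared baseline by itself establish a given correlation. If baseline and draw have equal standard deviations, it induces 0.5 when no baseline nicotine carries into later draws, but only 0.04/1.04 = 0.04 when 80% does.
- **That 40 participants are too few or the power figures wrong.** At an assumed, independent 5% loss with voided visits, precision is that of about 25–27 participants before dropout, still above the 20 used for power.
- **That computing totals from the remaining draws gives large bias.** At 5% random loss, on illustrative curves, it is about 2.5–5% of an AUC difference.

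The objection does not remove the QSU and MNWS problem. Both are taken six times per visit, have no stated summary, and fall under the subject-only model. A general promise to check assumptions supplies neither a within-visit term nor a rule for gaps.

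**Conclusion.** The point holds in a limited form. For outcomes measured repeatedly within a visit, the stated model does not hold its nominal level. The size in step 2 rests on assumed correlations of 0.1–0.5 and on time being modelled. For plasma nicotine it applies only if the rows are draws; for the QSU and MNWS it applies unless an unstated per-visit summary is used.

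Separately, the missing-at-random reason does not by itself cover a draw missed inside a visit total, although the plan foresees such draws. That loss rests wholly on an assumed rate and on independence between draws, and it is small at 1–2%.

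**What to change.** Name the analysis row for each outcome and match the model to it.

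- **Outcomes measured at each draw (QSU, MNWS, and plasma nicotine if analysed by draw).** Use product, time and product-by-time as fixed effects, with random effects for subject and for visit within subject, or an equivalent within-visit covariance. Check its adequacy: a visit intercept alone may not suffice if visit uptake is proportional to the curve. Enter the 0-minute value as a response row and do not subtract it from every draw; otherwise one missed baseline draw removes the whole visit.
- **Total nicotine delivery.** Either take the 0–90 minute trapezoidal contrast of the product-by-time means, with weights 2.5, 7.5, 12.5, 22.5, 30 and 15 minutes at 0, 5, 15, 30, 60 and 90 minutes (for a baseline-corrected total the 0-minute weight becomes 2.5 − 90 = −87.5), or keep a visit-level AUC with the random subject effect and state which draws must be present.
- **Maximum concentration.** It is not a linear contrast of the means, so keep it at visit level, state the required draws, and report visits lost by product.
- **Units.** Say which metric the 25.7 ng/mL refers to, since an AUC would be in ng·min/mL.

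The cost is one rewritten paragraph, with no added participants, visits or draws. Intervals will be wider where the subject-only model is too narrow, and the fuller model may need simplifying for the 15 participants of Aim 2. The planned 40 participants stay.

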Aim 1: This study will estimate the abuse liability of NPs with varying nicotine concentrations relative to cigarette smoking in a clinical study with Ohio Appalachian smokers by using a randomized crossover experimental design. Over the course of three clinic visits, N=40 adult cigarette smokers who live in Ohio Appalachia will: 1) smoke a usual brand cigarette, 2) use a 3mg nicotine concentration NP, and 3) use a 6mg nicotine concentration NP in our clinic; only one tobacco product will be used at each visit. We will measure nicotine pharmacokinetics, subjective effects, and intentions to use and switch to NPs. Our hypotheses are that (1a) both NPs will deliver less nicotine, and deliver it more slowly, than cigarette smoking and (1b) the 6mg nicotine NP will have greater nicotine delivery, be rated as more appealing, and have greater intentions for future use than the 3mg nicotine NP.

Aim 2: This study will examine the subjective and pharmacokinetic differences between tobacco-derived and synthetic NPs in adult cigarette smokers by using a randomized crossover experimental design. Over the course of three clinic visits, N=15 adult cigarette smokers who will: 1) use a 3mg tobacco-derived Zyn brand NP, 2) a 3mg synthetic Fre brand NP, and 3) a 3mg Niin brand synthetic NP in our clinic; only one product will be used at each visit. We will measure nicotine pharmacokinetics, subjective effects, and intentions to use and switch to NPs. Our hypotheses are that (1) tobacco-derived NPs will deliver nicotine more quickly and effectively than the synthetic NP and (2) the tobacco-derived NPs will be rated as more appealing and have greater intentions for future use than the synthetic NPs.

Intervention Impact

Aim 1: NPs are a novel tobacco product with potential to reduce or increase the harm of tobacco use in Appalachia. Evaluating NP abuse liability among Appalachian smokers will clarify the public health effect of NPs in Appalachian Ohio. Results will inform public health efforts, policy, and clinical care aimed at reducing tobacco-related disparities in Appalachia.

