Aim 2: The difference between tobacco-derived and synthetic NP on NPs' abuse liability is unknown. Tobacco-derived nicotine contains >99% of the S stereoisomer of nicotine, but most methods of manufacturing synthetic nicotine result in a racemic mixture of R- and S-nicotine stereoisomers.⁷⁸ NP manufacturers (as well as e-cigarette manufacturers including Puff Bar) that claim to use synthetic nicotine do not specify whether their nicotine solutions contain the racemic R/S-nicotine mixture, or if R-nicotine is omitted. Although less studied than S-nicotine, it is speculated that R-nicotine produces weaker biological effects because it is a 10-fold less potent agonist of nicotinic receptors.⁷⁸ In other words, we expect that NPs using synthetic nicotine vs. tobacco-derived nicotine will have a lower abuse liability—potentially making them less substitutable for cigarette smoking. Results from this work will provide the first evaluation of synthetic nicotine delivery via oral tobacco, informing public health efforts, policy, and future research in this emerging area of tobacco control.

Preliminary Research

For preliminary research, we evaluated characteristics of Appalachian adults enrolled in the Tobacco User Adult Cohort study. Compared to non-Appalachian tobacco users, Appalachian tobacco users initiated tobacco use and became regular users approximately one-year earlier, used tobacco more frequently, and had lower interest in cessation.¹⁵ Investigations into dual use found that a majority of Appalachian adults who used cigarettes and e-cigarettes were likely to transition to using cigarettes exclusively.³⁷ In other words, it appears that e-cigarettes were being used unsuccessfully by smokers trying to quit and that they were an inadequate complete substitute for smoking. Additionally, exclusive e-cigarette users were more likely than dual users to report that e-cigarettes are useful for quitting smoking and that e-cigarettes feel like smoking regular cigarettes.³⁸ *Conclusions: (1) Tobacco use behaviors vary between Appalachian and non-Appalachian adults, and thus evaluation of our research objectives in Ohio Appalachia is warranted; (2) uptake of novel tobacco products for smoking cessation (i.e., complete substitution) has been largely unsuccessful in Ohio Appalachia; and (3) exclusive use of novel tobacco products in Appalachia is associated with beliefs that the product is appealing and aids in smoking cessation.*

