We are also conducting a pilot observational study examining awareness of NPs, NP use, and exposure to NP marketing in Ohio adults. To date, we have enrolled 294 participants (32% smokers, 45% SLT users, 23% non-users) to complete a brief, online survey. Of the sample, 92% have agreed to be re-contacted for future studies—providing a source of recruitment for our proposed pilot. In preliminary analyses, nearly two-thirds (66%) of participants were aware of NPs, 38% had tried NPs, and 31% reported current NP use. Among smokers, awareness (65%) and trial (33%) of NPs were similar to the overall sample, and 25% reported current use. NP marketing exposure among smokers was also high (65% in the past year), with the most common sources of exposure being point of sale (35%), online/social media (29%), and

television (20%). *Conclusions: 1) Awareness and trial of NPs is growing among Ohio adults, including cigarette smokers; and 2) marketing exposure is common, supporting our rationale to extend this line of investigation to understand NP appeal and addictiveness in smokers in Appalachia.*

Aim 1 Study Objectives

Primary

- To estimate the abuse liability of NPs with varying nicotine concentrations relative to cigarette smoking.

Secondary

- To clarify the public health effect of NPs in Appalachian Ohio.

Exploratory

- To estimate the abuse liability of NPs with varying nicotine concentrations relative to cigarette smoking by measuring nicotine pharmacokinetics.
- To estimate the abuse liability of NPs with varying nicotine concentrations relative to cigarette smoking by measuring subjective effects.
- To estimate the abuse liability of NPs with varying nicotine concentrations relative to cigarette smoking by measuring intentions to use and switch to NPs.

Aim 2 Study Objectives

Primary

- To understand the pharmacokinetic difference between tobacco-derived and synthetic NPs.

Secondary

- To clarify the public health effect of NPs on adult smokers

Exploratory

- To understand the differences in abuse liability between tobacco-derived and synthetic NPs by measuring nicotine pharmacokinetics.
- To understand the differences in abuse liability between tobacco-derived and synthetic NPs by measuring subjective effects.
- To estimate the abuse liability of tobacco-derived vs. synthetic NPs by measuring intentions to use and switch to NPs.

2. Investigational Plan

Study Outline

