This study will recruit 40 adult cigarette smokers from Ohio Appalachia and surrounding rural areas (Aim 1) and 20 adult cigarette smokers from Ohio (Aim 2) for a randomized crossover study. Subjects will be recruited through social media advertisements; through our nicotine pouch pilot study, where participants agreed to future contact regarding other studies; and through outreach to our community partners: the OSUCCC's Community Outreach and

Engagement team and the Tobacco Free Ohio Alliance. Subjects will have an initial phone screen to confirm interest and eligibility and will then be invited to participate in 3 study visits in person visits at the Center for Tobacco Research.

Aim 1: Order of study clinic visits will be randomized. In random order, participants will 1) smoke one usual brand cigarette, 2) use one 3mg NP, and 3) use one 6mg NP. Research staff will measure nicotine pharmacokinetics, subjective effects, and intentions to use and switch to NPs through physiological data, lab values, and questionnaires.

Aim 2: Order of study clinic visits will be randomized. In random order, participants will use 1) Zyn wintergreen 3mg (tobacco-derived nicotine) 2) a Fre wintergreen 3mg (synthetic nicotine), and 3) a Niin wintergreen 3mg (synthetic nicotine). Research staff will measure nicotine pharmacokinetics, subjective effects, and intentions to use and switch to NPs through physiological data, lab values, and questionnaires.

Recruitment phase

Aim 1: We will recruit daily cigarette smokers who live in Ohio Appalachia and surrounding rural areas using social media advertisements, by re-contacting participants from our preliminary studies who agreed to take part in future studies, and through outreach via our community partners.

Geographically, recruitment advertising will be targeted to Ohio Appalachia counties (32 in total), surrounding rural counties close to Ohio Appalachia, with efforts focused on counties within one hour of Columbus.

Aim 2: We will recruit daily cigarette smokers using social media advertisements, by re-contacting participants from our preliminary studies who agreed to take part in future studies, and through outreach via our community partners.

Participants in Aim 2 may reside anywhere in Ohio, though recruitment efforts will be focused within one hour of Columbus.

Screening and scheduling phase

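### Aim 2 asks whether tobacco-derived and synthetic pouches differ, but the planned three-product test does not target that question, and with one tobacco-derived brand no analysis can separate nicotine source from brand

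*Combined protocol and SAP*

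**What the plan says.** The primary objective under Aim 2 Study Objectives is "To understand the pharmacokinetic difference between tobacco-derived and synthetic NPs". The Description and Rationale of Intervention section adds two directional hypotheses: that "tobacco-derived NPs will deliver nicotine more quickly and effectively than the synthetic NP", and that "the tobacco-derived NPs will be rated as more appealing and have greater intentions for future use than the synthetic NPs". The first refers to the synthetic product in the singular and the second in the plural.

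The Study Outline lists three wintergreen pouches labelled 3mg: Zyn (tobacco-derived), Fre and Niin (both synthetic). Under Intervention Impact, the lower abuse liability expected of synthetic pouches is attributed to the weaker receptor potency of R-nicotine. The same paragraph says that manufacturers "do not specify whether their nicotine solutions contain the racemic R/S-nicotine mixture, or if R-nicotine is omitted".

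Statistical Considerations plans linear or logistic mixed models to "assess the main effects of product on plasma nicotine delivery, subjective effects, and behavioral intentions", and then states "The same analysis strategy will be used for both aims". The only multiplicity figure comes after that sentence, inside the Aim 1 power calculation: "With a total sample size of only 20 participants and a Bonferroni-adjusted alpha of 0.017". For Aim 2 the section says that no data exist for a power calculation and that the 15 participants are meant to provide them.

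**The concern.** There are two gaps between the question and the plan.

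- **The test.** A main effect of product asks whether any of three means differ. Aim 2 asks whether Zyn differs from Fre and Niin in a stated direction. Analysts could answer it by the overall test, by three pairs at 0.017, by two Zyn comparisons, or by pooling the synthetics, and could reach different answers. Pooling is not a neutral default, because the protocol itself says the isomer content of synthetic products is not disclosed.
- **The interpretation.** With one brand on the tobacco-derived side, any Zyn difference is also a brand difference. Nothing in the documents limits the Aim 2 conclusion to the products tested, while the rationale rests on nicotine source. The estimates passed to future studies could then carry the wrong label.

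**Working it through.** **The plan's own figure.** 0.05/3 = 0.0167, which rounds to the stated 0.017, so it fits three pairwise comparisons at an assumed familywise 0.05 (0.05/2 = 0.025 does not fit). In Aim 1 the three pairs are exactly those that hypotheses 1a and 1b need: each pouch against the cigarette, and 6mg against 3mg. In Aim 2 the third pair, Fre against Niin, tests no hypothesis.

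**Inputs.** N=15 (Statistical Considerations); three products, each used once by each person; balanced subject-plus-product model with error df = 2 × 14 = 28. The unit is the within-person residual SD. Effect sizes are assumed.

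**1. The overall test can be significant with no Zyn contrast.** Put Zyn at 0, Fre at −h and Niin at +h. Zyn minus the synthetic mean is 0 − (−h + h)/2 = 0. The noncentrality of the overall F test is 15 × (0 + h² + h²) = 30h², which is above zero for any h other than 0.

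**2. Power when the hypothesis is true.** Put Zyn 0.8 SD above both synthetics, two-sided 0.05.
- Overall F: squared deviations sum to 0.64 × (4/9 + 1/9 + 1/9) = 0.427; noncentrality 15 × 0.427 = 6.4; power 56%.
- Zyn minus the synthetic mean: SE = √(1.5/15) = 0.316; noncentrality 0.8/0.316 = 2.53; power 69%.
- One Zyn pair: SE = √(2/15) = 0.365; noncentrality 2.19; power 56% at 0.05, 44% at 0.025, 38% at 0.017.
- Both Zyn pairs significant in the right direction (simulated): about 40%; at 1.1 SD, about 73%.

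**3. Precision.** The critical t on 28 df is 2.048. The 95% CI half-width is 2.048 × 0.365 = 0.75 SD for each Zyn pair and 2.048 × 0.316 = 0.65 SD for Zyn minus the synthetic mean. The Study Outline gives 20 for Aim 2 instead of 15; at 20 the pair half-width would be 0.64 SD.

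**4. Multiplicity if all three products are equal (simulated, per outcome).** At least one false Zyn difference, in either direction, occurs in about 9% of trials with two unadjusted tests, 4.6% with Holm over two, and 3.1% at 0.0167. If both comparisons must be significant in the hypothesised direction, the rate is 0.5% when all are equal. It cannot exceed 2.5% when Zyn equals either synthetic, because that comparison alone passes in only 2.5% of trials.

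**5. Source and brand.** A model with an intercept, a source term and three brand terms has 5 columns but rank 3, since three product means support only three parameters. Fre against Niin is the only information on brand variation; it has one degree of freedom and lies wholly on the synthetic side.

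To size this, assume no source effect and brand effects with SD r. The variance of Zyn minus the synthetic mean is then 1.5r² + 1.5/N, while the test allows only for 1.5/N. At N=15 the sampling part is 0.10 and the brand part is as follows:

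| r (residual SDs) | 1.5r² | Significant at 0.05, N=15 | Same, N=1000 |
|---|---|---|---|
| 0.25 | 0.094 | 15% | 81% |
| 0.5 | 0.375 | 36% | 90% |
| 1.0 | 1.5 | 61% | 95% |

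More participants make it worse, because the test becomes better at detecting a real brand difference.

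**The case against.** The case for leaving the plan alone has four parts.

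- **The contrasts are implied.** The hypotheses say which product should exceed which, and a mixed model supplies product coefficients, so pairwise comparisons may well be intended. That is fair: the plan does not rule them out. But it does not name them for Aim 2, and 0.017 is not stated as an analysis rule for either aim. On its own, the missing multiplicity rule is missing detail rather than an error.
- **The design already handles brand.** Flavour and labelled strength are matched and there are two synthetic brands. This narrows the confounding but cannot remove it. It is also true that no passage says a Zyn difference will be reported as a source effect. The point is that nothing prevents it and the rationale invites it.
- **A wrong conclusion is unlikely.** A reader might infer that the overall test would often give false support to Aim 2. With Fre and Niin assumed 0.5 SD either side of Zyn, it is significant in 64% of trials, and in 30% of trials it is significant while neither Zyn comparison passes Holm. Neither figure is a false-support rate. In that scenario the test is significant with Zyn highest in only 3.9% of trials, and Zyn is significantly above both synthetics in under 0.1%. An analyst who sees Zyn in the middle could not call a directional hypothesis supported.
- **Aim 2 is a small pilot.** It claims no power, which lowers the stakes. Hypothesis testing is still planned for it, however, and its purpose is to provide effect estimates, so those should match the question.

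**Conclusion.** The concern holds in two limited parts. First, the planned product effect is not a test of the Aim 2 hypotheses: it can respond to Fre against Niin alone, and at 0.8 SD it has 56% power against 69% for the direct pooled contrast. Second, a nicotine-source conclusion from this design would be unsound, because source is fully aliased with brand. With no source effect, the pooled contrast would be significant in 15% to 61% of trials over the assumed range of brand variation.

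The documents do not support the stronger readings that the plan commits to a source claim, excludes pairwise comparisons, or is likely to declare Aim 2 supported wrongly through the overall test. The scenarios rest on assumed SD units, a balanced model and N=15. The aliasing does not depend on any of these. The change is modest in weight and worth making before the Aim 2 data are analysed.

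**What to change.** **1. Wording.** In Intervention Impact and Aim 2 Study Objectives, describe Aim 2 as a comparison of three named products (Zyn, Fre and Niin, 3mg wintergreen), with nicotine source as one possible explanation. State that a Zyn difference will not be reported as a nicotine-source effect.

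**2. Analysis.** In Statistical Considerations, directly after the sentence that applies one strategy to both aims, add:

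> For Aim 2, the model-based contrasts Zyn minus Fre and Zyn minus Niin are reported with 95% CIs, with Zyn minus the mean of Fre and Niin, and Fre minus Niin, beside them. An Aim 2 hypothesis is called supported for an outcome only if both Zyn contrasts are significant at two-sided 0.05 in the hypothesised direction for that outcome (for example, shorter time to peak for faster delivery). No further adjustment is needed for this both-required rule. If a difference from a single brand is claimed, the two p-values are Holm-adjusted and the brand is named. A significant overall product effect alone does not answer Aim 2.

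The direction is set by outcome because a lower value favours a product on time to peak and on craving or withdrawal scores.

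**Cost.** A few sentences, with no new participants, visits or assays. The conclusion becomes more modest. The both-required rule is demanding at N=15: about 40% power at 0.8 SD and 73% at 1.1 SD if the synthetics are alike, which at 0.8 SD is below the overall test's 56%. The CIs will therefore carry most of the information, which suits a study meant to inform later ones. The Aim 2 sample size of 15 (which agrees with the stated total of 55 less 40 for Aim 1) should also be reconciled with the 20 in the Study Outline.
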